The goal of the interviews is to acquire specific information in order to adapt the MAPSS-MS intervention. During the interviews, data collectors (the PI and a research assistant) will probe for understanding as well as summarize participant statements for accuracy. Data collectors will also keep field notes of significant ideas and interview setting. The interview transcripts will be analyzed using Miles and Huberman’s method of content analysis. The PI and one other member of the research team will initially review the transcripts. The results of the initial coding will then be reviewed by the research team and finalized. Transcripts will be analyzed for common themes regarding sessions, content, and barriers to participation. The research team will meet to review those findings and make changes to the class sessions based on the findings. The adapted MAPSS-MS intervention will not be piloted until reviewed and approved by the IRB.

Phase 2: Intervention Pilot Testing Protocol

Participants involved in Phase 1 will be invited to join the Phase 2 of the study. Additional participants will be recruited to reach the desired sample size (n=20) for Phase 2 pilot testing. Phase 2 participants will be randomly assigned to an intervention group (n=10) or an “enhanced usual care” control group (n=10). Baseline questionnaire booklets (demographic data, functional status, MS self-management, and self-report surveys) will be mailed to all Phase 2 participants upon receipt of the

Research Proposal

signed consent form and the verification of clinically definite MS form signed by their healthcare provider. At baseline and 8-weeks (post-intervention), a trained research assistant (RA) will arrange to meet with each participant individually to administer the NIH Toolbox Cognitive Battery at a location of their choice (e.g. home). At this meeting, participants will also receive an accelerometer to wear on their non-dominant wrist for 7 days and 7 nights along with printed and verbal instructions on accelerometer wear and care. The data collectors will have received training on instrument administration and accelerometry. Postage-paid, preaddressed envelopes will be given to participants to return all study materials to the PI's research office at The University of Texas at Austin, School of Nursing.

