Participants randomly assigned to the intervention group (n=10) will remotely attend eight weekly 90-minute intervention sessions from the location of their choice (e.g., home) via their chosen device (computer, tablet, and/or smart phone) using a web-based video conference platform. The 10 intervention participants will be divided into 2 cohorts of 4 to 6 persons each. Participants in the “enhanced usual care” control group (n=10) will receive an illustrated instructional booklet on Physical Activity for persons with MS developed by the National Center on Health, Physical Activity and Disability (NCHPAD).

The eight weekly educational classes, originally developed for the MAPSS-MS intervention, will be adapted for remote web-based delivery (Appendix A). Specific intervention content will be modified based on feedback from Phase 1 interviews and research team members. Content will provide educational information emphasizing PA and include: (1) information on MS self-management strategies incorporating PA, fatigue, mood, and sleep self-monitoring; (2) assessment of cognitive problems; (3) resources and barriers to self-management; (4) goal setting and self-monitoring; and (5) lifestyle changes to maximize cognitive health. Phase 2 intervention content will follow the PA guidelines specifically designed for persons with MS developed by The Canadian Society for Exercise Physiology (Ginis & Hicks, 2007). These guidelines promote fitness benefits for adults with MS who have mild to moderate disability through “30 minutes of moderate-intensity aerobic activity (e.g. walking, housekeeping, gardening) 2 times per week and strength-training exercises for major muscle groups 2 times per week” (Latimer-Cheung, Martin Ginis, et al., 2013, p. 1829). All sessions will emphasize maximizing cognitive function in MS and address the interrelated effects of PA and other self-management skills on cognitive function.

Post-intervention data (questionnaire booklets, NIH Toolbox Cognitive Battery, and accelerometry) will be gathered, using the methods described for baseline data collection, within 2 weeks of the final intervention class for those in the intervention group. Those in the control group will complete post-intervention data 8-10 weeks after baseline data collection.

a. Location

The research will be performed at the University of Texas at Austin, School of Nursing and at locations chosen by each participant (e.g., their home).

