The PI and RAs have been trained in procedures to respect the rights of human subjects. There will be a special focus on issues related to 1) protecting privacy and confidentiality for participants randomized into the intervention group who will meet remotely in small groups (4-6 persons) via a web-based video conference platform on their chosen device - computer, tablet, and/or smart phone; and 2) awareness of fatigue and potential distress (related to concerns regarding cognitive and physical performance). Confidentiality and privacy of potential participants will be preserved, as the individual must contact the principal investigator to express interest in the study and disclose their name and contact information.

Research Proposal

Confidentiality of the Data or Samples

- a. Phase 1: An electronic recorder (e.g., Sony IC recorder) will be used to make electronic audio files of Phase 1 interviews. Audio files will be deleted from the recording device when transferred to UTBox cloud storage. UTBox has been approved by the Information Security Office for use with Confidential (formerly known as Category I) university data, including HIPAA data. Audio files will be named using the participant's unique ID number and the date recorded; no identifying data will be included or recorded from individual participants. De-identified audio files will be transcribed by a professional transcription service. Audio files stored on UTBox will be destroyed after they have been transcribed and the transcriptions reviewed by the PI and RA.
- b. Phase 2: After receipt of the signed consent and verification of MS diagnosis forms, participants will be mailed: 1) the questionnaire packet to complete at home with instructions (e.g., to take breaks as often as needed); 2) a postage-paid, preaddressed envelope to return the completed questionnaire packet to the PI's research office at The University of Texas at Austin, School of Nursing. A trained RA, blinded to the participant's group assignment, will collect the NIH Toolbox measures using an iPad at baseline and 8-weeks (post-intervention) at a location (e.g. home) selected by the participant. Accelerometer data will be downloaded directly from each device onto the PI's password-protected computer.

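### The assessor said to be blinded also arranges the 8-week cognitive visit, which is timed by a different rule in each arm, and nothing in the plan protects the blind

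*Protocol*

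**What the plan says.** Three statements in the Protocol bear on this point.

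- **The blind.** Section 7, Confidentiality of the Data or Samples, item b: "A trained RA, blinded to the participant's group assignment, will collect the NIH Toolbox measures using an iPad at baseline and 8-weeks".
- **Who arranges the visit.** Section 4, Phase 2: Intervention Pilot Testing Protocol, for both time points: "a trained research assistant (RA) will arrange to meet with each participant individually to administer the NIH Toolbox Cognitive Battery".
- **When the second visit is due.** The same part of section 4 sets the timing by arm. Intervention participants are assessed "within 2 weeks of the final intervention class for those in the intervention group". For the others: "Those in the control group will complete post-intervention data 8-10 weeks after baseline data collection". The rule covers the cognitive battery: "Post-intervention data (questionnaire booklets, NIH Toolbox Cognitive Battery, and accelerometry) will be gathered", by the same methods as at baseline.

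The Protocol does not say who holds the allocation, when randomisation happens relative to the baseline visit, or who tells the RA when a visit is due. It describes no instruction to participants to keep their group to themselves and no record of whether the RA learned it. The SAP does not mention blinding.

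**The concern.** One role is described as unaware of the assignment and is also given a task whose timing rule depends on the assignment. Someone booking the 8-week visit from the Protocol must know whether the participant had a final class, and when. That is the allocation.

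There is a second route. The visit is face to face, at a place the participant chooses, with someone who knows whether they had eight video classes or a booklet. Nothing asks them not to say so.

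The NIH Toolbox battery is the only objective measure of cognition and the only outcome for which the Protocol states a blinded assessor. If the examiner knows the arm, encouragement, prompting or the recording of spoken answers could differ between arms. The SAP will test group differences at alpha below 0.10, so a comparison could be reported as blinded when it was not. The ability to measure study outcomes is also a stated process outcome (section 3, Aim 2), so whether blinding survived is something this pilot could usefully learn.

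**Working it through.** The plan gives no figure to reproduce. There are two checks: whether the visit date itself shows the arm, and what an examiner bias would do.

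**1. The two windows on one time scale**

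Inputs from Protocol section 4:
- Intervention participants "will remotely attend eight weekly 90-minute intervention sessions", so first to last class is 7 × 7 = 49 days.
- Their window is 0 to 14 days after the last class.
- The control window is 8 to 10 weeks after baseline, which is day 56 to day 70.
- "The 10 intervention participants will be divided into 2 cohorts of 4 to 6 persons each", so the members of a cohort share one last-class date.

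Let g be the days from a participant's baseline visit to the first class. The documents do not give g, so it is ranged. The intervention window is day g + 49 to day g + 63.

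| g (days) | Intervention window | Control window | Overlap |
|---|---|---|---|
| 0 | 49–63 | 56–70 | 7 days |
| 7 | 56–70 | 56–70 | 14 days (identical) |
| 14 | 63–77 | 56–70 | 7 days |
| 18 | 67–81 | 56–70 | 3 days |
| 21 | 70–84 | 56–70 | day 70 only |
| 28 | 77–91 | 56–70 | none |
| 42 | 91–105 | 56–70 | none |

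At the baseline visit, "participants will also receive an accelerometer to wear on their non-dominant wrist for 7 days and 7 nights". If that wear must finish before class 1, g is at least 7. Because baseline visits are individual but a cohort starts together, g can differ within a cohort. As an illustration, if baseline visits are spread over 14 days and classes start 7 days after the last one, g runs from 7 to 21. That range goes from identical windows to one shared day.

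So with a prompt start the date need not show the arm. With a lag beyond 21 days, the interval since baseline does show it, to any RA who knows the baseline date and the two rules, whoever makes the booking.

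**2. What an examiner bias would do**

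The documents give no bias figure, so 0.1, 0.2 and 0.3 SD in favour of the intervention are assumptions, with no true effect.

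- SE of a standardised difference with 10 per arm: √(1/10 + 1/10) = 0.447 SD.
- Noncentral t with 18 degrees of freedom, noncentrality = bias / 0.447, tested at two-sided alpha 0.10.

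| Assumed bias (SD) | Noncentrality | Two-sided rejection | Rejection favouring the intervention |
|---|---|---|---|
| 0 | 0 | 0.100 | 0.050 |
| 0.1 | 0.224 | 0.108 | 0.076 |
| 0.2 | 0.447 | 0.131 | 0.112 |
| 0.3 | 0.671 | 0.170 | 0.159 |

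This is a simple t-test. The SAP specifies ANCOVA, so the figures are indicative only.

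**The case against.** The strongest reply is that the Protocol nowhere says the RA works out the due date. Arranging to meet someone is compatible with the office supplying a date or a window without the arm, and the sentence on collecting post-intervention data does not say who sets the timing. This stands. A reader might infer that the blind cannot hold as written, but the documents show an unprotected blind, not a proven contradiction. The reply does not remove the point, because the office-supplied date is itself a safeguard that the Protocol does not describe.

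Second, the windows can coincide. At g = 7, an RA who books everyone 8 to 10 weeks after baseline satisfies both rules without knowing any assignment, and for g from 0 to 14 at least 7 days are shared. This also stands. It defeats the reading that scheduling breaks the blind even when the windows match; in that case only disclosure by the participant remains.

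Third, one might argue that clustered cohort dates against scattered control dates would reveal the arm. The documents do not say when controls are enrolled. They could be enrolled alongside a cohort, and the intervention window is two weeks wide. This pattern is conjecture and carries no weight here.

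Fourth, the bias figures show what a bias would do, not that one is likely. All eight tests run on an iPad, and only two are named as oral. Nor is everything outside the Toolbox self-reported, since actigraphy gives objective sleep and activity measures. The point is confined to cognition.

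Finally, this is a feasibility pilot, and disclosure is a general hazard when participants know their group. That limits the severity but does not excuse claiming a blind without a procedure for it.

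**Conclusion.** The point holds in a limited form. The Protocol claims a blinded assessor, has that assessor arrange the visits, and times the second visit from a different anchor in each arm, with no safeguard described. The blind on the only objective cognitive outcome may therefore fail, through scheduling or through what participants say. The documents do not show that it must fail.

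Whether dates alone reveal the arm depends on the unstated lag from baseline to first class: not at 7 days, increasingly as the lag lengthens, and fully beyond 21 days. The consequence for the analysis is unknown. The range of about 0.11 to 0.17 for two-sided rejection rests wholly on assumed biases of 0.1 to 0.3 SD, applied uniformly, in a t-test with 10 per arm. The change is worth making because it is nearly free and protects a property the Protocol claims.

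**What to change.** Reconcile the two parts of section 4 with section 7, item b:

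1. **Separate booking from testing.** Name an existing unblinded staff member, not the testing RA, who holds the allocation and sets every 8-week appointment. The Protocol does not say who holds it now, so this must be stated. The RA receives only ID, date, time and place, and does not attend or support classes.
2. **Deal with the different anchors.** Where possible, book both arms within a range of days since baseline that satisfies both existing windows, for example by starting classes soon after the baseline week. For lags up to 21 days that range is from the later of day 56 and day g + 49 to the earlier of day 70 and day g + 63. Beyond 21 days there is none, and step 1 alone does not hide the arm.
3. **Limit disclosure.** Ask participants, in the appointment letter and at the start of the visit, not to mention classes or booklets. Give the Toolbox before anything else.
4. **Record what happened.** After each 8-week test the RA notes any disclosure and a guess of arm. Report both next to the Toolbox result.

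The cost is Protocol wording, a sentence in a letter, one item on the RA's form and a little scheduling work for existing staff. No new assessor, participant or analysis is needed.

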Official Title:

A Cognitive Self-Management Intervention for Persons with Multiple Sclerosis:
Adapting Web-based Technology

Statistical Analysis Plan

Results will be entered into a computer database for analysis using IBM SPSS Statistics version 25. Data will be checked for accuracy by research staff. Reliability estimates (internal consistency) will be determined for each instrument, and alphas of >0.70 will be considered acceptable. Descriptive analyses will be performed to obtain a description of the sample on demographic and illness-related variables. Analysis of covariance (ANCOVA) will be used to measure the differences between groups while controlling for continuous variables that might affect the outcome (e.g., age, length of diagnosis). The significance level for this pilot study will be alpha <0.10 . Feasibility measures will look for trends in the data focusing on recruitment and retention of participants over the 8-week intervention, problems and solutions encountered using the web-based video conferencing platform by the interventionist and/or the participants, wear ability of the ActiGraph wrist watches for seven days.

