The primary objective of this study is to develop and pilot test an innovative cognitive self-management intervention for PwMS delivered via web-based video conferencing. Data derived from interviews will be used to guide the adaptation of Stuifbergen's 8-week Memory, Attention, and Problem-Solving Skills in MS (MAPSS-MS) intervention to be delivered via web-based video conferencing. The adapted MAPSS-MS intervention will be feasibility tested in small groups of PwMS. Outcome variables include: (1) neurocognitive function assessed using the NIH Toolbox®, a comprehensive set of psychometrically sound neuro-behavioral measures¹⁸ that quickly assesses cognitive functions using an iPad, (2) objective PA and sleep using Actigraph™ accelerometers, (3) self-reported sleep, depression, and fatigue using the Patient-Reported Outcome Measurement Information System (PROMIS), and (4) MS specific self-management using the Multiple Sclerosis Self-Management Scale (MSSM). Community-residing PwMS, age 21 to 70, will be recruited from Central Texas to participate in Phase 1 interviews (n=5) and Phase 2 pilot testing (n=20) of the adapted version of the 8-week MAPSS-MS cognitive self-management intervention emphasizing PA delivered via web-based video conferencing. In Phase 2 pilot testing (n=20), an intervention group (n=10) will be compared to an "enhanced usual care" control group (n=10).

Research Proposal

The specific aims are to:

Aim 1: (a) Conduct interviews with PwMS to gather data to guide the adaptation of a tailored, cognitive self-management intervention delivered via web-based video conferencing, (b) Develop an adapted version of the 8-week MAPSS-MS intervention guided by the analysis of the interview data.

Aim 2: Conduct a feasibility study of the adapted MAPSS-MS cognitive self-management intervention emphasizing PA using objective and self-report data from community-residing PwMS. Process outcomes include success with recruitment, ability to deliver the intervention using web-based video conferencing, and ability to measure study outcomes.

4. Procedures

Study Design

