Phase 1 interviews will be conducted by the PI at a location selected by the participant (e.g. home).

Phase 2 data will be collected by mail (U.S. Postal service) and in-person at a location of the participants' choice (e.g. home). Participants will remotely attend eight weekly 90-minute intervention sessions from a location of their choice (e.g., home) via a web-based video conference platform on their chosen device (computer, tablet, and/or smart phone).

Research Proposal

b. Resources

External funding from the Center for Transdisciplinary Collaborative Research in Self-Management Science (National Institute of Nursing Research, National Institutes of Health, Grant: P30 NR0115335: PI [name]) at The University of Texas at Austin, School of Nursing is anticipated to start 9/1/2017.

c. Study Timeline

The estimated completion time for this study is 15 months. Data collection will begin in October of 2017 and continue through September of 2018 or study completion. Data analysis will be conducted from June to August of 2018 with report writing occurring from September through November of 2018.

5. Measures

The following measures will be used to collect data on the effectiveness of the intervention at the two data collection points with the exception of demographic information and MS functional status measure, which are baseline-only measures.

Phase 1 Measures

Interview questions have been designed specifically for this project.

Phase 2 Measures

The following measures will be used to collect data on the effectiveness of the intervention. Contextual factors and MS functional status will be collected at baseline only; the remaining measures will be collected at baseline and 8-weeks post intervention.

- 1) Contextual Factors – A Demographic Information Sheet will be used to collect baseline information on a variety of demographic (age, gender, education, marital status, ethnicity) and disease characteristics that will be used to describe the sample.

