- 2) MS Functional Status – The Self-Administered Expanded Disability Status Scale (EDSS) will be used to measure MS-related functional impairment. Derived from Kurtzke's (1983) physician-administered EDSS, the self-administered EDSS was developed by Bowen, Gibbons, Gianas, and Kraft (2001) for use in epidemiologic and longitudinal studies. The self-administered test was found to have strong intraclass correlation coefficients with the physician-administered EDSS using gait alone ($r = 0.89$) or gait plus functional systems ($r = 0.87$). While the EDSS has been the subject of both reliability and validity concerns, it is undeniably the most widely used method to quantify MS-related functional status by clinicians and researchers alike (Bowen et al., 2001; Schwartz, Vollmer, & Lee, 1999). Scores derived from the EDSS range from 0 (normal neurologic function) to 10 (death due to MS) with a score of 4.5 reflecting the ability to "walk without aid or rest for some 300 meters" (Kurtzke, 1983, p. 1446).
- 3) MS Self-Management – The Multiple Sclerosis Self-Management Scale-Revised (MSSM-R) is the only measure developed specifically to address self-management in persons with MS (Bishop & Frain, 2011). The 24-item scale has five-subscales: 1. Healthcare Provider Relationship and Communication (6 items); 2. Treatment Adherence/Barriers (7 items); 3. Social/Family Support (3 items); 4. MS Knowledge and Information (4 items); and 5. Health Maintenance Behavior (4-items). Total scores range from 0 to 100, with higher scores indicating a higher degree of MS self-management.

Research Proposal

- 4) Objective Cognitive Function – assessed with the NIH Toolbox Cognitive Battery – iPad App
(Time to administer the 8-measure battery: approximately 34 minutes)
 - a. Language - A set of mental processes that translate thought into symbols (words, gestures) that can be shared among individuals for purposes of communication. Tests focus on two aspects of language: 1) Vocabulary knowledge, measured by the Picture Vocabulary Test; and 2) Oral reading (decoding) skills, measured by the Oral Reading Recognition Test
 - i. NIH Toolbox Picture Vocabulary Test (4 minutes)
 - ii. NIH Toolbox Oral Reading Recognition Test (3 minutes)

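### The SAP sets a 0.10 significance level for between-group ANCOVA with no main outcome, no multiplicity control and no exploratory status, while the protocol lists many outcome measures

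*SAP*

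**What the plan says.** The SAP is a single paragraph. On the comparison of arms it says "Analysis of covariance (ANCOVA) will be used to measure the differences between groups", with continuous covariates given only as examples (age and length of diagnosis). It then says "The significance level for this pilot study will be alpha <0.10". It does not list the scores that enter ANCOVA, rank them, state whether tests are one- or two-sided, mention multiplicity, or describe the comparisons as exploratory.

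The protocol supplies the measures but not the analysis set:

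- Section 3 (Purpose) names the outcome variables by construct, for example "neurocognitive function assessed using the NIH Toolbox" and "self-reported sleep, depression, and fatigue using the Patient-Reported Outcome Measurement Information System (PROMIS".
- Section 5 (Measures) itemises them. The Toolbox entry reads "Time to administer the 8-measure battery: approximately 34 minutes", and the self-report entry describes seven short forms.
- The only ranking is inside the actigraphy sleep variables, where total sleep time is put first. That is not a study-wide main outcome.

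Section 5 twice describes the purpose of the measures. Its opening says they will "collect data on the effectiveness of the intervention at the two data collection points with the exception of demographic information", and Phase 2 Measures begins "The following measures will be used to collect data on the effectiveness of the intervention". Aim 2 is about feasibility: "Process outcomes include success with recruitment, ability to deliver the intervention using web-based video conferencing, and ability to measure study outcomes".

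**The concern.** A significance level needs a stated set of tests to apply to, and a statement of what a significant result may be taken to show. The SAP gives the level and neither of the other two. As written, any listed measure with p<0.10 could be reported as significant, on measures that the protocol ties to effectiveness, from 10 participants per arm.

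If one outcome is tested, the chance of a false significant result is 0.10. If many are tested at the same level, it is far higher. The reader of the eventual report could not tell from the plan which case applies, or whether the outcomes highlighted were chosen after the data were seen. What is at stake is the meaning of the between-group p-values. Recruitment, delivery and measurement feasibility are not touched.

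**Working it through.** **The plan's own figure.** The only stated figure is the level, 0.10. One test at 0.10 has a false-positive chance of 0.10. The documents give no power, effect size, study-wide error rate or number of tests to reproduce.

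**Inputs from the documents.** Level 0.10 (SAP); 20 participants, 10 per arm (protocol section 4, Study Design); measures from protocol sections 3 and 5.

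**Assumptions.** The level applies to each test; tests are two-sided; every counted outcome is tested; no true difference exists on any of them. The correlations between outcomes are assumed, because the documents give none.

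**Counting the outcomes.** The documents allow several counts:

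- 7, by construct in section 3: neurocognition 1 + physical activity 1 + objective sleep 1 + self-reported sleep, depression and fatigue 3 + self-management 1. This is itself a reading, since no cognitive composite is defined.
- 14, with each Toolbox test separate: 8 + 1 + 1 + 3 + 1.
- 18, with the four further actigraphy sleep variables: 14 + 4.
- 22, with all seven short forms rather than three: 18 + 4.
- 23, with activity counts and steps separate: 22 + 1.
- 28, if the five MSSM-R subscales are added: 23 + 5.

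**Formulas.** For k tests, the expected number of false positives is 0.10 × k. The chance of at least one, if the tests are independent, is 1 − 0.9^k. For correlated outcomes, null data were simulated with 10 per arm, equal correlation between outcomes and two-sided tests at 0.10 (two-sample t tests, 18 degrees of freedom, 100,000 replicates, Monte Carlo standard error at most 0.0016).

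| Outcomes tested | Expected false positives | Independent | Correlation 0.3 | 0.5 | 0.7 |
|---|---|---|---|---|---|
| 1 | 0.1 | 0.10 | – | – | – |
| 7 | 0.7 | 1 − 0.9^7 = 0.522 | 0.478 | 0.410 | 0.323 |
| 14 | 1.4 | 1 − 0.9^14 = 0.771 | 0.692 | 0.579 | 0.438 |
| 18 | 1.8 | 1 − 0.9^18 = 0.850 | 0.766 | 0.647 | 0.478 |
| 23 | 2.3 | 1 − 0.9^23 = 0.911 | 0.835 | 0.705 | 0.521 |

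For 28 outcomes the independent figure is 1 − 0.9^28 = 0.948, with 2.8 expected false positives.

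**Check with the planned method.** Simulating ANCOVA with two continuous covariates unrelated to the outcome (16 degrees of freedom, 40,000 replicates, standard error at most 0.0025) gives, at correlations 0.3 / 0.5 / 0.7, 0.481 / 0.409 / 0.327 for 7 outcomes and 0.833 / 0.709 / 0.517 for 23. The two set-ups agree within 0.01, so the result does not depend on using ANCOVA rather than a t test.

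**Reading the table.** Every case with 7 or more outcomes is at least about three times 0.10. The chance exceeds one half for 14 or more outcomes up to correlation 0.5, but is below one half for 7 outcomes at correlation 0.3 or more.

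**The case against.** The strongest reply is that the study already signals its status. The significance sentence refers to a pilot, section 3 gives the objective as developing and pilot testing the intervention, and section 4 calls it a pilot feasibility study. There is no efficacy hypothesis, no power claim and no progression rule tied to p<0.10. This stands as a limit on severity. It does not close the gap: the SAP still sets a significance rule, and the pilot label does not say what p<0.10 may be taken to show.

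Second, *effectiveness* is used loosely. The Phase 2 sentence introduces a list that includes the demographic sheet and a baseline-only disability scale, neither of which can measure effectiveness. This also stands. A reader might infer that the plan intends to declare effectiveness at p<0.10; no text says so. The point is only that nothing rules it out.

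Third, the per-test reading and the counts are inferences. Testing every listed measure is not stated; activity counts and steps are things the device stores; and section 4 speaks of one objective activity measure. All of this is correct, which is why the result is given as a range. A reader might infer that 23 tests are planned, or that the trial's error rate is 0.91. The documents support neither.

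Fourth, naming one outcome does not by itself secure 0.10, because the covariates are only examples. A null simulation that took the smallest p over the four models with or without age and length of diagnosis gave 0.13 to 0.15. Letting the baseline score in or out as well gave 0.18 to 0.21. These are worst cases of free choice under assumed correlations, but they show that the covariate set must be fixed too. The 0.10 also assumes independent participants, while the intervention arm is taught in two cohorts (section 4, Phase 2).

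**Conclusion.** The point holds as a minor one. Read per test, and if all listed outcomes are tested with no true difference, the plan's rule gives a chance of at least one p<0.10 of about 0.5 for 7 outcomes and 0.9 for 23 under independence. At assumed correlations of 0.7 to 0.3 the ranges are about 0.3 to 0.5 and 0.5 to 0.8. The independence figures are the upper end, since these outcomes are likely to be correlated.

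Two stronger conclusions might be drawn, and neither is supported. One is that 0.10 is the wrong level for a pilot: the level is acceptable, and what is missing is a set of tests and a limit on interpretation. The other is that the study's main purpose is undermined: the process outcomes under Aim 2 are not judged by these tests and are unaffected.

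**What to change.** Replace the SAP's significance sentence with:

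> Between-group results will be reported for all listed outcomes as adjusted mean differences with 90% confidence intervals and are exploratory; no claim of effectiveness will be based on p<0.10 or on an interval excluding zero.

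Also:

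- List in the SAP the outcomes to be analysed by ANCOVA, and fix the covariate set in advance.
- Align the two sentences in protocol section 5 that speak of effectiveness.
- If a formal 0.10 test is kept, limit it to one outcome and one covariate set named before the data are analysed. Its nominal error rate is then 0.10, assuming independent participants.

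A 90% interval that excludes zero is the same test as two-sided p<0.10, so the gain comes from giving up the claim and not from the interval itself.

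The cost is wording in the SAP and two sentences in the protocol. Data collection and sample size do not change. The downside is that the pilot gives up scattered p<0.10 claims.
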